## 7.2 Participant Withdrawal from the Study and Replacement

Participants are free to withdraw from participation in the study at any time upon request. Subjects may also withdraw voluntarily from receiving the study intervention for any reason.

Subjects will have approximately a 48-hour window to decide if they would like to drop out of the study and leave the confinement unit before challenge. The investigator should be explicit regarding study follow-up (*e.g.*, safety follow-up) that might be carried out once the subject undergoes challenge but decides to leave the confinement unit before discharge criteria are met.

Subjects will be strongly discouraged from withdrawing from the study post-challenge. Any subjects who withdraw from the study post-challenge but prior to meeting the discharge criteria outlined will be asked to sign a document stating that they are aware of the potential risks of developing influenza complications, they are aware of the risks of transmitting influenza virus to high-risk populations, and that they will stay sequestered in their homes and avoid contact with others until they have two consecutive negative tests for influenza virus by qualitative RT-PCR conducted at least 12 hours apart. The PI, co-investigator or study team will counsel the subject on infection control practices to minimize any community transmission. Subjects without two consecutive days of negative tests for influenza virus by qualitative RT-PCR will be given one dose of baloxavir marboxil or a 5-day course of oseltamivir at the time of premature withdrawal from the study. For the purposes of safety and serological testing, the subject will also be asked to come for all follow-up visits. If the subject leaves the confinement unit prior to Study Day 8, whether or not they are continuing to shed virus, the subject will be encouraged to return for follow-up visits per outpatient schedule (i.e., Visits 9, 10, and 11). If the subject does not return for scheduled follow-up visits, extensive effort (i.e., at least three documented contact attempts via phone calls, e-mails, text message, or private social media communication, etc., as voluntarily provided by the subject and based on IRB recommendations, made on at least 3 separate days and followed by a certified letter if unsuccessful) will be made to locate the subject and reiterate that follow-up visits are strongly encouraged for safety reasons. These efforts will be documented in the subjects' records. See the MOP for Subject Contact Information. The investigator will inform the subject that already collected data will be retained and analyzed even if the subject withdraws from this study. If a subject withdraws or is withdrawn prior to completion of the study, the reason for this decision must be recorded in the case report forms (CRFs).

An investigator may discontinue or withdraw a participant from the study for the following reasons:

- Subject becomes pregnant.
- Study non-compliance that, in the opinion of the investigator, poses an increased risk (i.e., missing safety labs), or compromises the validity of the data.
- If any clinical adverse event (AE), laboratory abnormality, or other medical condition or situation occurs such that continued participation in the study would not be in the best interest of the participant.
- Any subject that experiences a related SAE during the confinement unit period.
  - This includes any subject who develops a severe influenza complication (Section 2.3.1) during the confinement unit period and requires admission to an Intensive Care Unit (ICU), and/or receipt of ICU level of care
- If the participant met an exclusion criterion for participation in the study (either newly developed or not previously recognized) that precludes further study participation
- Medical disease or condition, or new clinical finding(s) for which continued participation, in the opinion of the investigator, might compromise the safety of the subject, interfere with the subject's successful completion of this study, or interfere with the evaluation of responses
- Subject becomes lost to follow-up.

Protocol 20-0005	Version 8.0
H3N2 Dose-Ranging Challenge	04May2023

If the subject agrees, every attempt will be made to follow all AEs through resolution.

Subjects who withdraw, or are withdrawn from this study, or are lost to follow-up after signing the informed consent form (ICF) and administration of the study product will not be replaced. Subjects who withdraw, or are withdrawn from this study, or are lost to follow-up after signing the ICF but before randomization may be replaced.

The reason for participant discontinuation or withdrawal from the study will be recorded on the Case Report Form (CRF).

#### 7.3 Lost to Follow-Up

A participant will be considered lost to follow-up if he or she fails to return for scheduled visits and is unable to be contacted by the study site staff.

## 8. STUDY ASSESSMENTS AND PROCEDURES

#### 8.1 Screening and Outcome Procedures

#### 8.1.1 Screening Procedures

Potentially eligible study subjects may be pre-screened under an active screening protocol (DMID 20-0004) to identify those with HAI antibody titers  $\leq$ 1:40 specific to the challenge virus strain. Additionally, potentially eligible subjects may be recruited through other site registries, advertisements or by word-of-mouth. During the study screening period (Day -45 to Day -3), participants who meet all inclusion criteria and none of the exclusion criteria are eligible for enrollment to the study. Participants will be screened during the screening period and again at the time of confinement (Day -2).

After the informed consent, the following assessments are performed to determine eligibility and obtain baseline data:

- Take a focused medical history, including the following information:
  - History of any chronic medical conditions related to inclusion and exclusion criteria
  - Review of receipt of 2020/2021 influenza vaccine and 2021/2022 influenza vaccine (note that receipt of 2020/2021 influenza vaccine and receipt of 2021/2022 influenza vaccine within the past 4 months or within approximately 57 days post-challenge is exclusionary)
  - Concomitant medications taken within 90 days prior to signing the ICF will be reviewed with subjects to determine stability of chronic diseases and eligibility
- Women of childbearing potential must have a negative serum HCG pregnancy test at screening and a negative urine HCG pregnancy test on Day -2.
- Participants must have a negative drug urine toxicology test (amphetamines, cocaine, and opiates) at screening and on Day -2 (amphetamines, cocaine, and opiates), unless the drug is deemed acceptable by the Investigator.
- Physical exam (standard exam at screening and targeted exam on Day -2)
- Height measurement
- Weight measurement
- Vital signs measurement (including RR, HR, BP, oral temperature)
- SpO2 measurement
- ECG
- Baseline posterior anterior (PA) and lateral CXR (Among women of childbearing potential, a repeat urine pregnancy test will be performed locally if >7 days have passed since the negative serum pregnancy test was drawn. The result of the urine pregnancy test must be negative before the CXR is performed.)
- Blood for laboratory evaluations (approximately 15 mL at screening only):
  - Serology at screening: HIV, Hepatitis B surface antigen, Hepatitis C antibody,
  - Chemistry at screening: alanine transaminase (ALT) and creatinine (Cr)
  - Hematology at screening: white blood cells (WBCs), absolute lymphocyte count, hemoglobin, and platelets

- Blood for HAI titer
- Participants must have a negative qualitative multiplex respiratory virus assay (BIOFIRE® FILMARRAY® respiratory panel by bioMérieux or Luminex xTAG®) including a test for SARS-CoV-2 on NP swab on Day -2 in order to be eligible for influenza challenge
- Nasopharyngeal swab for virologic assessments

Clinical screening laboratory evaluations and the HAI titer will be performed locally by the site laboratory. The volume of venous blood to be collected is presented in **Appendix C**.

The overall eligibility of the subject to participate in the study will be assessed once all screening values are available.

#### 8.1.2 Discharge from Quarantine

Subjects will be discharged from quarantine on or after Study Day 8 once they meet all of the following discharge criteria (subjects meeting discharge criteria may leave after receipt of qualitative RT-PCR results for the day). Subjects who do not meet discharge criteria on Study Day 8 will remain in the confinement unit until the criteria are met. Study procedures for the confinement unit will be the same as on Study Day 8, except no additional blood draws unless clinically indicated.

- Have two consecutive qualitative RT-PCR tests on NP swabs (collected 12 hours apart on Study Day 6 or thereafter on consecutive days) that are negative for influenza A using a multiplex respiratory virus assay (BIOFIRE® FILMARRAY® respiratory panel by bioMérieux or Luminex xTAG®).
- Are afebrile (< 100.6°F/38.1°C).
- $SpO_2 \ge 95\%$  on room air
- Show no moderate or severe influenza signs or symptoms by clinical evaluation.
- Are clinically stable for at least 48 hours (per the evaluation of the licensed study clinician listed of the Form FDA 1572).
- All AEs and SAEs will be recorded on the appropriate DCF.

#### 8.1.3 Procedures to be Followed in the Event of Abnormal Laboratory Test Values or Abnormal Clinical Findings

If a physiologic parameter, e.g., vital signs, is outside of the protocol-specified range, then the measurement may be repeated once if, in the judgment of the investigator, the abnormality is the result of an acute, short-term, rapidly reversible condition (e.g., stress, anxiety, or "white coat syndrome"). A physiologic parameter may also be repeated if there is a technical problem with the measurement caused by malfunctioning, or an inappropriate measuring device (i.e., inappropriate-sized blood pressure cuff).

A subject may be re-screened if there is a transient disease status (e.g., subject complained of a "cold or fever" and met a temporary delaying enrollment criterion of acute illness or fever), or if a protocol eligibility criterion that is not met at the initial time of screening, will be met by re-screening at a later date (e.g., a medication taken within exclusionary window at the time of first screening that would not be within exclusionary window at a later rescreen).

No subject may be screened more than twice for the same challenge cohort due to a screening failure result as defined above. However, subjects that screen fail for one challenge cohort can be screened in the future for another challenge cohort.

Participants will be provided the results of any abnormal clinical laboratory results and will be referred to their primary healthcare provider. Research laboratory results will not be provided to the participant.

#### 8.1.4 Outcome / Immunogenicity / Genetic Assessments

The specific timing of procedures/evaluations to be done at each study visit are captured in Section 1.2, Schedule of Activities (SoA). All labs in this section will be completed in research labs, thus not requiring CLIA certification. Instructions for specimen preparation, handling, and storage are included in the protocol-specific MOP. Specimen shipment to designated research laboratories for outcome/immunogenicity/genetic assessments will occur at intervals during the course of this study following all applicable International Air Transport Association (IATA) requirements and according to the specifics for storage temperature and documentation as detailed in the protocol-specific MOP.

#### 8.1.4.1 Outcome Evaluations

#### **Clinical assessments**

- Symptomatic influenza infection for determining AR will be assessed using a Modified Jackson score collected by study staff twice a day (approximately 8 AM and after 3 PM) from Day -2 until the time of discharge. The investigator will also complete the Modified Jackson Score at the Day 15 visit to assess any ongoing symptoms. The Modified Jackson score will be calculated after evaluation of vital signs, laboratory results, and the Modified Jackson score across multiple days. The score will be calculated during analysis for safety reporting by the SDMCC.
- An additional validated, patient-reported outcome (PRO) measure to standardize assessment of influenza symptoms in clinical research (i.e., FLU-PRO Survey Instrument and Validation Diary) will be completed by subjects once a day (after 3:00 PM) from Day -2 through Day 15. The investigators will review the FLU-PRO and Validation Diary at the Day 15 visit to assess any ongoing symptoms.
- Wearable devices
  - The Garmin uses PPG technology along with mechanical sensors to measure heart rate, oxygen saturation, activity, etc.
  - The Oura Ring uses PPG technology along with mechanical sensors to measure heart rate, body temperature, activity, etc.

• The Faros device has an ECG sensor and accelerometer and can be worn using cable/electrode connections.

#### Virologic assessments

Virologic assessments will be done at screening (Days -45 to -3), baseline (Days -2 and -1) and will be repeated daily from Days 2-8 during the confinement period or for a longer period if still RT-PCR positive for influenza on Days 7 or 8 until two negative swabs are confirmed, at least 12 hours apart, consecutively. Only qualitative RT-PCR will be performed at the screening visit.

- Qualitative multiplex respiratory virus assay (BIOFIRE® FILMARRAY® respiratory panel by bioMérieux or Luminex xTAG®) on NP swab(s).
- Quantitative RT-PCR for influenza from NP swab(s) specimen.
- Qualitative and quantitative RT-PCR for influenza from NLF specimens may be performed.
- Quantitative viral culture from NP swab(s) and/or NLF specimens may be performed.

#### 8.1.4.2 Immunogenicity Assessments

- HAI, MN, NAI, anti-HA-stalk antibody titers from serum
- sIgA titers from NLF
- Systemic cytokines and chemokines from serum
- Mucosal cytokines and chemokines from NLF or nasal curettage specimens
- Transcriptional responses from whole blood
- Plasmablasts (ASC) in circulation (from PBMC)
- Influenza-specific B and T cell immune responses from PBMCs
- T cell activation may be performed in cells isolated from nasal curettages
- Immunophenotyping of innate, B and T cell subsets in NLF or nasal curettage specimens

Please see Appendix C for venipuncture volumes.

#### 8.1.4.3 Genetic/Genomic Analyses

- Human leukocyte antigen (HLA) class I and II alleles from blood
- Transcriptional responses from whole blood

Please see Appendix C for venipuncture volumes.

#### **Genetic Privacy and Confidentiality**

Genetic data and health information may be stored and shared with other researchers through a controlled-access repository, such as dbGaP. There may be a risk that information resulting from research genetic testing could be misused for discriminatory purposes. However, state and federal laws provide some protections against genetic discrimination. Researchers who will have access to genetic information will take measures to maintain the confidentiality of the information. HLA genetic testing will be performed for research purposes only and will not be performed by a CLIA certified laboratory. Therefore, the results of HLA testing will not be shared with subjects.

#### Management of Results and Genetic Counseling

Subjects will be contacted if a clinically actionable gene variant is discovered either as part of this protocol or a related sub-study. Clinically actionable findings for the purpose of this study are defined as disorders appearing in the American College of Medical Genetics and Genomics recommendations for the return of incidental findings that is current at the time of primary analysis. Subjects will be contacted at this time with a request to provide a blood sample to be sent to a CLIA certified laboratory. If the research findings are verified in the CLIA certified lab, the subject will be offered the opportunity to come back to have genetic education and counseling to explain this result. If the subject does not want to come back, a referral to a local genetic healthcare provider will be provided (at their expense).

This is the only time during the course of the study that incidental findings will be returned. No interrogations regarding clinically actionable findings will be made after the primary analysis.

#### 8.2 Safety and Other Assessments

Study procedures are specified in the SoA. A study clinician licensed to make medical diagnoses and listed on the 1572 will be responsible for all trial-related medical decisions. Specimens for clinical screening and safety laboratory evaluations will be transported from the participating clinic sites or confinement units to the respective site's certified clinical laboratories or on-site certified laboratories for analysis.

#### **Physical Examination**

A physical exam will be conducted at screening (Day -45 to -3) by a licensed study clinician listed on the Form FDA 1572. A more targeted physical examination will be conducted at prechallenge screen (Day -2), pre-challenge baseline (Day -1), viral challenge (Days 1-8), and follow-up (Days 15, 29, 57). The targeted physical exam will include evaluation of the oral/pharyngeal, neck, lung, and heart exams. An otoscopic exam will be performed as part of the targeted physical exam at baseline (Day -1) and as needed. Additional clinical evaluation will be performed if clinically indicated.

#### Vital Signs

Vital signs will be assessed at screening (Day -45 to -3), pre-challenge screen (Day -2), prechallenge baseline (Day -1), pre-challenge baseline (Day 1 prior to challenge), post-challenge (Days 1-8) approximately within each 8-hour period (i.e., three times per day), and follow-up (Days 15, 29, 57). Vital signs will include pulse, systolic blood pressure, diastolic blood pressure, respiratory rate, and oral temperature.

#### SpO2

SpO2will be assessed at screening (Day -45 to -3), pre-challenge screen (Day -2), pre-challenge baseline (Day -1), pre-challenge baseline (Day 1 prior to challenge), post-challenge (Days 1-8) approximately within each 8-hour period (i.e., three times per day) and follow-up (Days 15, 29, 57).

#### Electrocardiograms (ECGs)

A 12-lead ECG will be performed at screening (Day -45 to -3), post-challenge (Day 6), and as clinically indicated and confirmed by the PI or designated clinician licensed to make medical diagnoses and listed on Form FDA 1572. Screening ECGs must be within normal reference ranges or deemed not clinically significant.

#### Chest X-Ray (CXR)

A PA and lateral CXR will be performed at screening (Day -45 to -3).

**Clinical Laboratory Evaluations** 

- Serology at screening: HIV, Hepatitis B surface antigen, Hepatitis C antibody, and HAI titer
- Hematology (at screening and study Days 2, 4, and 8): white blood cells (WBCs), absolute lymphocyte count, hemoglobin, and platelets
- Chemistry at (as screening and study Days 2, 4, and 8): alanine transaminase (ALT) and creatinine (Cr)
- A urine toxicology test (amphetamines, cocaine, and opiates,) at screening and on the day of admission to the confinement unit (amphetamines, cocaine, and opiates)
- Serum HCG pregnancy test at screening
- Urine HCG pregnancy test (for female subjects of childbearing potential) to be done before the baseline CXR (if > 7 days have passed since the negative serum pregnancy test was drawn) and on Day -2, to be performed locally.
- Qualitative multiplex respiratory virus assay (BIOFIRE® FILMARRAY® respiratory panel by bioMérieux or Luminex xTAG®), including SARS-CoV-2 RT-PCR, on NP swab(s) at screening and on Day -2 and Day -1 in order to remain on the unit for challenge and daily from Day 2 through the confinement period.

#### 8.2.1 Procedures to be Followed in the Event of Abnormal Laboratory Test Values or Abnormal Clinical Findings

The site PI or designated clinician licensed to make medical diagnoses and listed on Form FDA 1572 is responsible for recording all AE/SAEs that are observed or reported during this study, regardless of relationship to study product. AE/SAEs, abnormal laboratory test values or abnormal clinical findings will be collected, assessed, documented, reported, and followed appropriately, using a local laboratory as necessary. In determining eligibility, refer to Section 5.1 and 5.2, and the protocol-specific MOP.

Signs, symptoms, laboratory findings that are part of mild to moderate influenza disease collected as part of the Modified Jackson Score, in addition to mild or moderate fever and lymphopenia from the time of challenge through 7 days post-challenge, will not be considered adverse events (AEs). These signs, symptoms, and laboratory findings (mild and moderate) include the following: runny nose, stuffy nose, sneezing, sore throat, headache, cough, malaise (tiredness), body aches, chills, feverish, shortness of breath, earache, fever, and lymphopenia. Mild to moderate fever is defined in Appendix A and mild to moderate lymphopenia is defined in Appendix B. Influenza infection related symptoms that are deemed by the investigator to be severe, in addition to severe fever as defined in Appendix A and severe lymphopenia as defined in Appendix B, will be considered as adverse events. Symptoms as assessed by the FLU-PRO will not be assessed as adverse events unless deemed by the investigator to be severe.

Safety will be assessed by the frequency and severity of:

- 1. Study product-related serious adverse events occurring from the time of the challenge through the end of the study (approximately 2 months post-challenge).
- 2. Clinical safety laboratory adverse events occurring from the time of challenge through Study Day 8. Parameters to be evaluated include: white blood cells (WBCs), absolute lymphocyte count, hemoglobin, platelets, and alanine transaminase (ALT), and creatinine (Cr).
- 3. Adverse Events non-serious adverse events occurring from the time of challenge through approximately 28 days post-challenge. See below for how adverse events are defined.

#### 8.3 Adverse Events and Serious Adverse Events

#### 8.3.1 Definition of Adverse Events (AE)

ICH E6 defines an AE as any untoward medical occurrence in a patient or clinical investigation subject administered a pharmaceutical product regardless of its causal relationship to the study treatment. FDA defines an AE as any untoward medical occurrence associated with the use of a drug in humans, whether or not considered drug related (21 CFR 312.32 (a)).

An AE can therefore be any unfavorable and unintended sign (including an abnormal laboratory finding), symptom, or disease temporally associated with the use of medicinal (investigational) product. The occurrence of an AE may come to the attention of study personnel during study visits and interviews of a study recipient presenting for medical care, or upon review by a study monitor.

In this study, solicited symptoms of symptomatic influenza infection will be collected from the time of challenge through 7 days post-challenge and will **not** be considered adverse events. Objective clinical examination findings consistent with the solicited symptom, such as oropharyngeal erythema or lymphadenopathy, will also **not** be considered AEs. Any influenza signs, symptoms or lab findings determined by the clinician to have exceeded the expected severity or any moderate or severe complications, as listed in Section 2.3.1, will be considered

unsolicited adverse events and captured on the appropriate data collection form and electronic case report form (eCRF). Events that are not consistent with illness due to influenza will be considered unsolicited AEs as well. Events that occur after administration of antivirals will also be considered unsolicited AEs. Information to be collected for AEs includes event description, date of onset, assessment of severity, relationship to study product and alternate etiology (assessed only by those with the training and authority to make a diagnosis and listed on the Form FDA 1572 as an investigator), date of resolution, seriousness and outcome. AEs occurring during the study will be documented appropriately regardless of relationship. AEs will be followed through resolution. Resolution of an AE is defined as the return to pretreatment status or stabilization of the condition with the expectation that it will remain chronic.

Any chronic or stable medical condition that is present at the time that the subject is screened will be considered as baseline and not reported as an AE. However, if the severity of any preexisting medical condition increases, it should be recorded as an AE.

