#### 8.3.3 Time Period and Frequency for Event Assessment and Follow-Up

In this study, solicited symptoms of influenza infection will be collected from the time of challenge through 7 days post-challenge and will **not** be considered adverse events.

Any influenza signs, symptoms or lab findings determined by the clinician to have exceeded the expected severity of a mild or moderate influenza symptom or sign will be considered unsolicited adverse events and captured on the appropriate data collection form and electronic case report form (eCRF). Events that are not consistent with illness due to influenza will be considered unsolicited AEs as well. Unsolicited AEs will be captured starting at the time of challenge through 28 days post-challenge. Information to be collected for AEs includes event description, date of onset, assessment of severity, relationship to study product and alternate etiology (assessed only by those with the training and authority to make a diagnosis and listed on the Form FDA 1572 as an investigator), date of resolution, seriousness and outcome. AEs occurring during the study will be documented appropriately regardless of relationship. AEs will be followed through resolution. Resolution of an AE is defined as the return to pretreatment status or stabilization of the condition with the expectation that it will remain chronic.

Any chronic or stable medical condition (Section 5.1) that is present at the time that the subject is screened will be considered as baseline and not reported as an AE. However, if the severity of any pre-existing medical condition increases, it should be recorded as an AE.

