#### 9.5.3 Analysis of the Secondary Endpoints

# 9.5.3.1 Analysis of Secondary Endpoints

Assessing the safety profile of the challenge virus is a secondary objective of the study. This will be measured by the number of adverse events reported and the percentage of subjects reporting adverse events through Day 29, and the number of serious adverse events and the percentage of subjects reporting adverse events through Day 57.

Influenza signs and symptoms and clinical lab findings determined to have exceeded the expected severity will be considered unsolicited adverse events. Events that are not consistent with illness due to influenza and abnormal vital signs will be considered unsolicited AEs as well. Solicited signs and symptoms of influenza as described in Section 4.1 will not be considered AEs. The severity (mild, moderate, or severe) of abnormal vital signs and clinical laboratory values will be presented according to the toxicity grading scales in Appendices A, B and C. Other events will be reported according to the criteria in Section 8.3.2.1. Relationship with receipt of the challenge virus will be assessed as described in Section 8.3.2.2.

The frequencies of AEs through Day 29 and SAEs through Day 57 will be presented by MedDRA® system organ class (SOC) and preferred term (PT), severity, relationship to challenge virus, challenge dose group, and across all subjects receiving active virus. Incidence will be assessed by the number and percentage of subjects in each challenge dose group ever reporting an event, along with associated 95% CI for the probability of the event. To further assess the safety of the challenge virus, the incidence of any related moderate or severe AE and any SAE will be calculated for each challenge dose group and compared as described in Section 9.5.1.

Adverse events and clinical laboratory results will be presented in data listings. Analyses of safety endpoints will be performed for the Safety population.

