4.6.2. Safety Variables

Safety is assessed by the incidence, frequency, and severity of:

1. Study product-related serious adverse events occurring from the time of the challenge through the end of the study (approximately 2 months post-challenge).
2. Clinical safety laboratory adverse events occurring from the time of challenge through Study Day 8. Parameters to be evaluated include: white blood cells (WBCs), absolute lymphocyte count, hemoglobin, platelets, and alanine transaminase (ALT), and creatinine (Cr).
3. Adverse Events (AEs) – non-serious adverse events occurring from the time of challenge through approximately 28 days post-challenge.

Unsolicited Adverse Events

The FDA defines an AE as any untoward medical occurrence associated with the use of a drug in humans, whether or not considered drug related (21 CFR 312.32 (a)). An AE can therefore be any unfavorable and unintended sign (including an abnormal laboratory finding), symptom, or disease temporally associated with the use of medicinal (investigational) product.

In this study, solicited symptoms of symptomatic influenza infection are collected from the time of challenge through 7 days post-challenge and will not be considered adverse events. Objective clinical examination findings consistent with the solicited symptom, such as oropharyngeal erythema or lymphadenopathy, will also not be considered AEs. Any influenza signs, symptoms or lab findings determined by the clinician to have exceeded the expected severity or any moderate or severe complications, as listed in Section 2.3.1 of the protocol, are considered unsolicited adverse events. Events that are not consistent with illness due to influenza, and events that occur after administration of antivirals, are considered unsolicited AEs as well. Note that there are no solicited AEs for this study.

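### The protocol and SAP do not settle whether a non-severe influenza or FLU-PRO symptom after an antiviral is an adverse event; read literally, the antiviral clause ties AE rates by dose group to antiviral receipt

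*Protocol*

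**What the plan says.** Five sections define which influenza symptoms are AEs.

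- Protocol 8.2.1 covers mild or moderate Modified Jackson findings together with "mild or moderate fever and lymphopenia from the time of challenge through 7 days post-challenge, will not be considered adverse events (AEs"). It attaches no condition. Challenge is Day 1, so the window closes on Study Day 8. It adds, without an end date, that "Symptoms as assessed by the FLU-PRO will not be assessed as adverse events unless deemed by the investigator to be severe".
- Protocol 8.3.1 gives the same exemption for solicited symptoms and then lists further categories that are AEs. The last is: "Events that occur after administration of antivirals will also be considered unsolicited AEs".
- Protocol 8.3.3 says that "solicited symptoms of influenza infection will be collected from the time of challenge through 7 days post-challenge and will" not count as AEs. It repeats the other categories but not the antiviral one.
- Protocol 9.5.3.1, which sets out the safety analysis, says: "Solicited signs and symptoms of influenza as described in Section 4.1 will not be considered AEs". It gives no time window and no exception.
- SAP 4.6.2 follows 8.3.1: it gives the exemption, then says that "events that occur after administration of antivirals, are considered unsolicited AEs as well".

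The Schedule of Activities (note 8) and section 4.1 let antiviral treatment start on Day 6. The secondary safety endpoints are the number of AEs and the percentage of participants with any AE through Day 29. SAP Tables 57-60 show AEs by challenge dose group. Protocol 9.5.3.1 also compares related moderate or severe AEs, and SAEs, between dose groups. Neither document separates AEs by onset before or after an antiviral.

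**The concern.** The exemption and the antiviral clause overlap on Days 6-8. Take a mild runny nose on Day 7 in a participant who took an antiviral on Day 6. It is not an AE under 8.2.1, 8.3.3 or 9.5.3.1, but it is one under the literal words of the last category in 8.3.1 and SAP 4.6.2. The same symptom in an untreated participant through Day 8 is not an AE under any section.

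The overlap lasts longer for FLU-PRO, which is completed through Day 15. Section 2.3.1 quotes nausea (10%), vomiting (9%) and diarrhea (7%) for oseltamivir. These are FLU-PRO items but not Jackson items. A non-severe one reported in the diary after treatment is left out under 8.2.1 and counted under 8.3.1. The separate category for events not consistent with influenza does not clearly settle this, because 2.3.1 also lists nausea and diarrhea as minor influenza symptoms.

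Antiviral receipt is decided after challenge, by continued positivity or symptoms. Section 9.3.2 assumes that the attack rate, which combines shedding and symptoms, rises with dose. If receipt also rises with dose, the literal rule counts ordinary influenza symptoms as AEs more often at higher doses, and dose groups could differ in AE incidence with no difference in safety.

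**Working it through.** **The plan's own figure.** Protocol Table 3 gives the chance of seeing at least one safety event, 1 - (1 - p)^n. At p = 10% and n = 10, 15, 20 and 30 this is 65.1%, 79.4%, 87.8% and 95.8%, as printed; the other rows reproduce too. The table is correct, but it does not bear on how an event is classified.

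**Which rule applies on Days 6-8 after an antiviral?**

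| Section | Mild or moderate solicited symptom |
|---|---|
| Protocol 8.2.1 | Not an AE |
| Protocol 8.3.3 | Not an AE |
| Protocol 9.5.3.1 | Not an AE |
| Protocol 8.3.1 | Exempt by one sentence, an AE by a later one; precedence not stated |
| SAP 4.6.2 | As 8.3.1 |

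**Illustration of the literal rule.** Let b be the true background AE rate, equal in both dose groups; s the share given an antiviral in time to matter; and m the chance that a treated participant has a mild or moderate solicited symptom counted as an AE after the first dose. Treating background AEs and counted symptoms as independent:

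- incidence = 1 - (1 - b)(1 - s·m)
- spurious difference = (1 - b)(s_high - s_low)·m

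The documents give no value for b, s or m, so all three are assumptions. With b = 10%, s = 20% and m = 0.3, incidence is 1 - 0.90 × 0.94 = 15.4%. With s = 50% it is 1 - 0.90 × 0.85 = 23.5%.

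The last column is the exact probability that a two-sided Fisher test at 0.05 rejects, with 12 participants (Cohort 1A, active) against 34 (2 × 17, the 10^6 group).

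| s, low vs high | m | Incidence, low vs high | Difference (points) | Fisher rejection |
|---|---|---|---|---|
| any | 0 | 10.0% vs 10.0% | 0 | 2.2% |
| 20% vs 50% | 0.3 | 15.4% vs 23.5% | 8.1 | 4.1% |
| 20% vs 50% | 0.6 | 20.8% vs 37.0% | 16.2 | 11.3% |
| 20% vs 50% | 0.9 | 26.2% vs 50.5% | 24.3 | 25.6% |
| 20% vs 70% | 0.3 | 15.4% vs 28.9% | 13.5 | 8.6% |
| 20% vs 70% | 0.6 | 20.8% vs 47.8% | 27.0 | 31.2% |
| 20% vs 70% | 0.9 | 26.2% vs 66.7% | 40.5 | 67.8% |
| 40% vs 40% | 0.3-0.9 | equal | 0 | 3.0-3.8% |

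At b = 20% the difference runs from 0.80 × 0.30 × 0.3 = 7.2 points to 0.80 × 0.50 × 0.9 = 36.0 points. The artefact vanishes if m = 0 or if treatment is equal across doses.

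**The case against.** The strongest reply is that 8.3.1 does not contradict 8.2.1. It states the exemption itself, with emphasis, before listing further AE categories, so its events after antivirals may mean only events outside the exempt set. On that reading all five sections agree for Jackson symptoms. Conversely, 8.2.1 says "See below for how adverse events are defined", so 8.3.1 could be the intended exception. Both readings are reasonable. Neither is written down, and they give opposite answers. What stands is that a reader might infer a flat contradiction with a certain bias, and the text does not support that: the bias arises only if the clause is applied literally.

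Other parts of the reply also stand:

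- The size rests wholly on assumed inputs. Treatment that starts after Day 6 shrinks the overlap for Jackson symptoms.
- The 9.3.2 assumption concerns attack rate, not positivity at Day 6. Section 4.1 also offers treatment to those who remain symptomatic, so sham or uninfected participants can qualify.
- The study is not designed for formal group comparisons, and SAP 5.8 calls the analysis primarily descriptive. The comparison in 9.5.3.1 leaves out mild events. Moderate ones can enter, since 8.3.2.3 tells assessors always to suspect the study product.
- AE review is separate from the FLU-PRO diary, so nothing in 8.2.1 stops nausea elicited there from being recorded. The diary sentence leaves the point unclear; it does not forbid recording.
- Table 59 splits Days 1-8 from Day 9 onward, and Listings 12 and 17 let a reader trace events to antivirals. Neither table nor listing isolates the effect by dose group.

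**Conclusion.** The AE status of non-severe solicited and FLU-PRO symptoms after an antiviral is unresolved, and it should be settled before AE rates are read by dose. Under the literal clause, the number and percentage with AEs through Day 29, and the related moderate or severe comparison, partly reflect who was still positive or symptomatic and was treated.

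The size cannot be calculated from the documents. The range of about 8-41 percentage points assumes 20% versus 50-70% treated, a 10% background rate and a 30-90% chance of a counted symptom. It describes the percentage with any AE. For the related moderate or severe comparison m would be smaller, because mild symptoms drop out.

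A reader might infer three stronger things that the documents do not support:

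- That study halting is distorted. The AE-count halting rule in 7.1.1 uses grade 3 events, and the symptoms at issue are mild or moderate.
- That the two sites already classify identical symptoms differently. The manual of procedures and data collection forms are not available, so this is a possibility only.
- That shedding alone drives the effect. Section 4.1 also admits symptoms.

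**What to change.** 1. State one rule for solicited and FLU-PRO symptoms after an antiviral, in the same terms in Protocol 8.2.1, 8.3.1, 8.3.3 and 9.5.3.1 and SAP 4.6.2, and apply it the same way at both sites.
2. In SAP Tables 57-60 and the 9.5.3.1 comparison, show AEs with onset before, and on or after, the first antiviral dose separately by challenge dose group. AE onset and concomitant-medication dates are already collected.
3. Base the dose comparison on AEs defined independently of antiviral receipt, and show post-antiviral solicited symptoms separately. Dropping those symptoms altogether would be simpler, but it would lose information: 2.3.1 also quotes headache, cough and fatigue for oseltamivir and headache for baloxavir, and these overlap with Jackson items.
4. Reconcile the antiviral triggers in Schedule of Activities note 8 (two consecutive negative swabs not reached by Day 6), section 4.1 (symptoms and/or a positive test on Day 6) and section 6.5.1 (two consecutive negative days not reached by Day 8). No view is taken here on which is right.

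The cost is wording, one derived flag and extra table columns. The headline AE count may fall. Dates alone cannot order an event and a first dose on the same day, so the convention for these must be stated. Relationship to the antiviral is not a collected field; only relationship to study product and alternate etiology are, so the split shows timing, not cause.
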